***(All advertising must be submitted for review in its final printed/recorded form)**

Note: Attach copies of ALL recruitment materials in the attachment Section

Flyers/posters

Internet ads/postings

Email

Face to face interactions

Is there any possibility that potential participants may feel coerced to participate?

No

Is there any possibility that potential participants may feel undue influence to participate?

No

Participant Compensation/Costs

Will participants be compensated?

Yes

Form of Compensation

Gift Card/Certificate/Voucher

What is the approximate monetary value?

\$44 for the Intervention surveys, possibility to win \$25 for completing a podcast survey

Describe the remuneration plan.

Subjects will be paid for each survey they complete according to the following payment plan: \$8 outcome survey 1 \$10 outcome survey 2 \$10 outcome survey 3 \$10 outcome survey 4 \$6 mentoring group satisfaction survey

Subjects who complete podcast satisfaction surveys will be entered into a drawing each month to win one of two \$25 Amazon gift cards.

Will a 1099 be issued?

No

Will participants incur any costs to participate in this research?

Yes

Explain. This should be clearly outlined in the consent form.

Study participants will all have signed up to participate in the DadSpace mentoring program at the Women's Clinic of Northern Colorado. As with other classes WCNC offers, there is a fee to participate in the program. Class fees have not yet been set, but classes of similar length at The Women's Clinic run \$90.

Risks and Benefits

Minimal risk "means that the probability and magnitude of harm or discomfort anticipated in the research are not greater in and of themselves than those ordinarily encountered in daily life or during the performance of routine physical or psychological examinations or tests." [Department of Health and Human Services 45 CFR 46.102(j)]

Please indicate the researchers' evaluation of the overall risk level, and describe all known risks or discomforts associated with the study procedures, as prompted below. Note that any risks identified here should be consistent with risks you will disclose to participants in the consent process.

Minimal Risk

Are there risks associated with physical well-being?

No

Are there risks associated with psychological well-being?

Yes

Please describe.

While the level of risk is minimal, participants may become uncomfortable with some questions related to their experiences. They are allowed to decline to answer any question they feel uncomfortable with.

Are there risks associated with economic well-being, including employability?

No

Are there risks associated with social well-being, including reputational risks?

Yes

Please describe.

In a group setting, it is possible people in the group will know each other. If participants are not comfortable sharing their experiences during the group, they can choose not to say anything or remove themselves from the group.

Describe how the benefits of the research justify the likely risks to participants.

The group program and podcasts are research-informed to promote well-being and social support. Though psychological and social risks are possible, the risk is minimal compared to the potential benefits of participating in a program aimed at supporting fathers' successful adjustment before and after having a baby.

Describe direct research benefits to the participants, if any.

Risks in this study are minimal. The mentoring program and podcasts are designed to support positive outcomes in well-being and parenting for participants and their families. It is likely that any potential distress caused by surveys or social well-being will be outweighed by the benefits of the intervention and the supportive social environment.

Describe the indirect research benefits to society.

At the community level, the research may help refine the DadSpace mentoring program such that it becomes a sustainable and ongoing program to increase support resources for fathers. If the program is found to be feasible and efficacious, it may also help to inform future research for supportive fathering interventions. It is also possible the mentoring program could be adopted by other communities. Since podcasts are easily disseminated to a wide audience, podcasts may be useful to a variety of listeners, including perinatal fathers and those who help support them.

Data management plans, including plans for data sharing, are integral to project development. How you decide to collect, store, share and/or destroy data impacts your consent process, research procedures, data analysis, and publication.

Responses in this section constitute your plan. For guidance on how to answer these questions and plan for the data lifecycle, reference the resources and tools listed here.

[Data Management Services at CSU Libraries](#)

[General guidance and unfunded projects](#) (DMPTool)

[Funder-specific guidance and templates](#) (DMPTool)

If you choose to create a standalone data management plan (DMP) for your own purposes or at the direction of a funding agency, please attach that document to your protocol, also.

A [DMP fillable template](#) is available from CSU Libraries.

How will the data be stored and backed up during the research?

Initially, data will be managed and stored on Co-PI [name]'s password-protected Qualtrics account. Data will be downloaded from Qualtrics to a password-protected file folder in a secure HDFS research drive for statistical analyses (e.g., SPSS, Mplus). Access to this folder will only be granted to study personnel. Both Qualtrics and the PI's personal account are secure storage systems that are backed up regularly. A metadata repository will be developed for each study that describes the source of the data, a codebook for the demographic questions, syntax for computation of scale scores, and types of data files available (e.g., Excel, SPSS).

Who will be responsible for data and access management, and security?

Data Access Responsibility

[name]

Data Access Responsibility

[name]

Data Access Responsibility

[name]

Who will have access to study records or specimens?

Personnel

[name]

Personnel

[name]

Personnel

[name]

Will any external personnel have access to study records or specimens?

Yes

Please identify the external personnel with access to study records/data

WCNC staff ([name], [name], and [name]) will have access to participants' contact information and associated participant ID numbers. They will not have access to research data (survey data) associated with each participant ID.

How will you share the data?

Data outcomes will be reported in aggregate through reports to stakeholders and manuscripts. The availability of the data sets will be communicated to research peers and at conferences, and referenced in publications. The embargo period for the data sets restricting public access will be for two years from completion of the studies, and will be implemented in CSU's Digital Repository. Afterward, materials will be made available via persistent URLs configured for discovery by all major web crawlers.

Will identifiable data collected as part of the research be released in identifiable form? (e.g., pictures, recordings, responses to research questions, quotes)

No

Will the identifying information be destroyed at a specific date? For guidance, please reference any associated contract or grant (if applicable) and/or the [CSU Research Data Policy](#).

Yes

Destruction Date

August 1, 2031

What is the long-term preservation plan for the dataset?

After 2 years from completion of our study, we will archive the data in CSU's digital repository. We have no plans to submit data for open source access because as a CCTSI-funded project, the expectation is that we will use our findings to secure a larger extramural grant.

Do you intend to deposit your research data/specimens into a repository for future use?

Yes

If you already have a plan, please describe. Otherwise, you can enter N/A.

The data and related materials will be stored and preserved in CSU's open access digital institutional repository, a service jointly provided, operated, and managed by the CSU Libraries and the Department of Academic Computing and Networking Services. Because the total materials are <=1 TB in size, they will be stored, preserved, and made accessible at no cost to the project. The PIs will evaluate, distill, and select the data for preservation, and supply traditional and contextual metadata that will be reviewed and augmented as appropriate by librarians who are experts in digital repositories, including data and metadata organization and management. The CSU Digital Repository provides an exceptionally high-quality environment for data discovery, accessibility, transmissibility, and preservation. The CSU Libraries faculty and staff are experts in operating, managing, and sustaining digital data in formal repositories, possessing experience with multiple metadata schemes, harvesting of metadata and crawling of digital objects, digital rights management, and preservation.

Consent/Accord

Consent

The informed consent process involves presenting potential research participants with the key elements of a research study and what their participation will involve before they decide whether to participate. Please visit the [IRB website](#) for templates and guidelines on what information to include.

The default process for gaining consent is to use a signed form. Knowing that this does not always make sense, the IRB can approve alterations to what information is included, waive the requirement to get a signature or waive the requirement to obtain consent altogether when the request meets specific criteria.

Follow the prompts below to describe all consent processes and provide justification for any requested alterations or waivers.

Will informed consent be obtained from all research subjects (and/or their parents or legally authorized representatives)?

Yes

CSU Consent Personnel

[name]

No

Are you requesting a waiver of documentation of consent?

No

Consent

You do not have any procedures that include deception. If you are going to deceive or incompletely inform any subjects about any aspect of this study describe in the procedures section.

List each consent process

Who will obtain subjects consent?

Personnel

[name]

Which participant group is this consent process for?

All participants who agree to be involved in the mentoring program

How is consent being obtained?

WCNC staff will send a link to the electronic screener and study consent form to those who have signed up to participate in the mentoring group. [name] will confirm eligibility and receipt of consent and provide consent data to The Women's Clinic to house with participant identifiers.

Will non-English speaking participants be enrolled?

No

Program facilitation is being provided in English as with other programs WCNC offers, so it stands to reason that all participants will be able to understand and speak English.

Are any subjects unable to legally provide consent?

No

Conflict of Interests

For guidance on how to answer these questions and information please visit the [CSU Conflict of Interest page](#).

Does the research involve a drug, device, or biological invented by you, an immediate family member or other Research Personnel?

No

Is the research sponsored by an entity with which you, an immediate family member, or other Research Personnel have a paid consulting or advising relationship?

No

Will you, members of your immediate family, or other Research Personnel receive special compensation or increased compensation if the research generates a favorable outcome?

No

Will you, members of your immediate family, or other Research Personnel receive any money, gift or anything of monetary value above and beyond the actual costs of enrollment, conduct of the research, and reporting on the results, including, but not limited to, finders fees, referral fees, recruitment bonuses, and an enrollment bonus for reaching an accrual goal or similar types of payments?

No

Do you, members of your immediate family or other Research Personnel have any other interests or relationships (including volunteer services) that might constitute a conflict of interest or an appearance of conflict of interest in connection with the research project?

No

Will the payment you receive for services provided during the conduct of the research (e.g., investigator and Research Personnel time and tests) be inconsistent with fair market value for those services?

No

Significant Financial Interest: Please check Yes or No for each item below.

Will you, your immediate family members or other Research Personnel receive salaries, royalties and/or other payments for services (e.g., consulting fees, honoraria, research design, management position, independent contractor, service on advisory or review committees, board membership seminars, lectures or teaching engagements when totaled together exceeded \$5,000 during the previous 12 months or are expected to exceed \$5,000 over the next 12 months)? This excludes reasonable costs of conducting the research, as specified in the research agreement.

No

Do you, your immediate family members, or other Research Personnel hold any ownership interests including stocks, bonds, or stock options that exceed \$5,000 and/or that constitute more than a five percent (5%) ownership interest in the sponsoring organization? This does not include any interests held solely by reason of investment in a business by a mutual, pension or other institutional investment fund over which the investigator and/or his or her immediate family do not exercise day-to-day control of investment decisions.

No

Minimizing Risks and Disclosure to Subjects

Have you disclosed any actual, potential or perceived conflicts of interest in the consent form? Research Personnel are required to disclose all such conflicts to all research participants in the research consent form.

Yes

By submitting this form, you are attesting that you have read [Colorado State University's policy on Conflict of Interest](#) and agree to abide by its terms. You will update this disclosure form when new or changes in conflict of interest arise, and that you will comply with any conflict management plan required by the Institutional Review Board (IRB) to manage, reduce, or eliminate any actual or potential conflict of interest for the duration of the research.

Attachments

Attach all relevant documentation to your research in this section. Please label each item appropriately, so your IRB reviewers understand the purpose and population each document aims to address. Please delete the existing attachment and upload the Tracked Changes version and Clean revised document for review to update or revise any existing attachments.

Any documentation that a participant will see must be reviewed and approved by the IRB, including consent, recruitment, communications, tools, instruments, etc. Additional documents required for review include funding proposals, contracts, letters of agreement, methodology, related approvals, etc. For more information and guidance on what documentation to attach, please visit the IRB website.

Answers within your application indicate that the following documentation is required:

Attachment Type

Data Management Plan

Attachment

[DATA MANAGEMENT PLAN DADSPACE.DOCX](#)

Name

Data Management Plan

Attachment Type

Recruitment Materials

Attachment

[DADSPACE STUDY FLYER.PNG](#)

Name

Study Flyer

Attachment Type

Recruitment Materials

Attachment

[DADSPACE STUDY SOCIAL MEDIA IMAGE.PNG](#)

Name

Social Media recruitment image

Attachment Type

Recruitment Materials

Attachment

[RECRUITMENT COPY_UPDATED.DOCX](#)

Name

Recruitment wording

Attachment Type

Screening Tool or Procedure

Attachment

[SCREENER QUESTIONS.DOCX](#)

Name

Screening questions

Attachment Type

Other

Attachment

[DADSPACE MEASURES_FINAL.DOC](#)

Name

Survey measures

Attachment Type

Other

Attachment

[DADSPACE RESOURCE GUIDE.PDF](#)

Name

Referral resource guide

Attachment Type

Grant or Contract

Attachment Type

Grant or Contract

Attachment

[[name]-[name] 2021 CE PILOT GRANT PROPOSAL.PDF](#)

Name

Grant proposal

Attachment Type

Other

Attachment Type

Other

Attachment Type

Consent

Attachment

[DADSPACE MENTORING GROUP CONSENT FORM_REVISEDFORIRB.DOC](#)

Name

Attachment Type

Other

Attachment Type

Consent

Attachment

PODCAST SURVEY ONLINE CONSENT.DOC

Name

Anonymous Podcast Survey Online Consent Form

Attachment Type

Other

Statistical Design and Power

Study Title: DadSpace: Increasing Community Support Resources for Perinatal Fathers

Study ID: 1754

Date of Plan: 6/14/2021

Statistical Design and Power

We anticipate that by the conclusion of the DadSpace program feasibility trial, 28 fathers will have completed the program as well as pretests and posttests, and 28 fathers will have completed pre- and posttests as wait-list controls. With a moderate effect size of Cohen's $d = .50$, this sample size will provide power = .95 using a 2 (time) by 2 (group) repeated measures ANOVA with stability coefficients of $r = .50$. Power will be lower but still sufficient (.81) to detect a small/moderate effect size of $d = .33$. Given that pilot trials of DadSpace (e.g., *Becoming Fathers*) and focus groups have indicated that DadSpace is likely to be effective, we believe that effect sizes of .40-.50 are likely on each of the primary outcome measures.

In section 4.2, we entered multiple "additional measures," all of which assess program implementation. These measures provide us with feedback as to how the DadSpace program was delivered and received by the participants. Following best practices (e.g., Berkel et al., 2011), this information will serve two purposes: to provide guidance on strengthening the DadSpace program, and to assess how variations in implementation are related to degree of program impact. In order to assess the latter, exploratory correlational analyses will be conducted between implementation variables and gain scores on the pre-/posttest measures of program impact.

<https://doi.org/10.1007/s11121-010-0186-1>

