Any contact with participants to provide referrals will be noted and tracked by the staff member.

Will any video, photography, or audio be recorded as part of this procedure?

No

Will data be collected anonymously?

No

Privacy and Confidentiality

Explain how the established data management plan along with consent processes and other elements of the research design address the following.

Privacy is considered from the perspective of the participant and is a right to be protected. Privacy refers to an individual's interest in controlling others' access to themselves.

Based on their privacy interests, participants may want to control:

- The time and place where they give information
- The nature of the information they give
- Who receives and can use the information

For example, persons might not want to be seen entering a place that might stigmatize them, such as a pregnancy-counseling center identified as such by signs on the front of the building.

Describe how you will protect subject's privacy.

Participants will be able to complete electronic surveys in locations they are comfortable with, as chosen by the participant. Participants who attend the small-group mentoring program will be associating with a business they have already chosen to be affiliated with prior to being recruited for the study. If a participant is not comfortable attending the program due to its location or the other group participants, they may choose to stop attending the mentoring program at any time. Participants who complete the podcast survey will be able to provide their responses anonymously.

Confidentiality is about data. Confidentiality pertains to protecting information from disclosure based on an agreement between the participant and the researcher. When an individual shares information in a relationship of trust and expects it to be kept private or will be disclosed only with specific permissions, researchers must uphold this agreement and maintain data appropriately.

Describe how you will maintain the confidentiality of subjects' information.

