Identifiable information will only be accessible to WCNC staff. WCNC staff will provide ID numbers to each participant to use for completing their surveys. Research staff will only have access to participant ID numbers paired with survey data, not participant names or contact information. Survey responses will be aggregated for the purposes of reporting to community partners, stakeholders, publications, and grant reports. Given the small sample size, it is possible a person's data could be linked to their demographic information. To mitigate this risk, any data reported by demographic will be withheld if the demographic subgrouping contains a population of 3 or fewer people.

Clinical Trial

Will participants will be prospectively assigned to one or more interventions (including placebo or other control)?

Yes

Will the study evaluate the effects of the intervention on health-related outcomes (biomedical or behavioral)?

Yes

Does this study involve an FDA-regulated drug or device?

No

Will the study be conducted as a
Single-Site Clinical Trial

Will this study be posted on ClinicalTrials.gov?

Yes

ClinicalTrials.gov Registration# (or pending)

Pending

Additional information and support available through CSU Quality Assurance:

[contact]

Participant Population

Are you interacting or intervening with participants?

Yes

Provide an estimate of the anticipated participant total.

56

Are you analyzing existing data records or biospecimens?

No

Inclusion and Exclusion Criteria (e.g., Participants must have 20/20 vision, Participants must be 30-45 years of age, etc.) This should match your screening, consent, and recruitment materials.

Please list all inclusion criteria

Participants must be expecting a baby or have a baby less than one year of age and have signed up to participate in the DadSpace mentoring program at WCNC

Please list all exclusion criteria

Less than 18 years of age, non-English-speaking.

What is the rationale for studying the requested group(s) of participants?

These participants comprise the target population of people served by the clinic and the primary focus of the intervention.

Will you use a screening procedure, instruments, tools, questionnaires etc.?

Yes

Describe any planned screening procedures. Attach your screening document(s) (e.g., health history questionnaire), if applicable at the end of the form.

Participants will be screened for inclusion and exclusion criteria as listed above. Screening questions are attached.

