While the level of risk is minimal, participants may become uncomfortable with some questions related to their experiences. They are allowed to decline to answer any question they feel uncomfortable with.

Are there risks associated with economic well-being, including employability?

No

Are there risks associated with social well-being, including reputational risks?

Yes

Please describe.

In a group setting, it is possible people in the group will know each other. If participants are not comfortable sharing their experiences during the group, they can choose not to say anything or remove themselves from the group.

Describe how the benefits of the research justify the likely risks to participants.

The group program and podcasts are research-informed to promote well-being and social support. Though psychological and social risks are possible, the risk is minimal compared to the potential benefits of participating in a program aimed at supporting fathers' successful adjustment before and after having a baby.

Describe direct research benefits to the participants, if any.

Risks in this study are minimal. The mentoring program and podcasts are designed to support positive outcomes in well-being and parenting for participants and their families. It is likely that any potential distress caused by surveys or social well-being will be outweighed by the benefits of the intervention and the supportive social environment.

Describe the indirect research benefits to society.

At the community level, the research may help refine the DadSpace mentoring program such that it becomes a sustainable and ongoing program to increase support resources for fathers. If the program is found to be feasible and efficacious, it may also help to inform future research for supportive fathering interventions. It is also possible the mentoring program could be adopted by other communities. Since podcasts are easily disseminated to a wide audience, podcasts may be useful to a variety of listeners, including perinatal fathers and those who help support them.

Data management plans, including plans for data sharing, are integral to project development. How you decide to collect, store, share and/or destroy data impacts your consent process, research procedures, data analysis, and publication.

Responses in this section constitute your plan. For guidance on how to answer these questions and plan for the data lifecycle, reference the resources and tools listed here.

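### Power rests on 28 program-and-test completers against 28 test completers, equal to the protocol's whole estimated total, and the supplied text names no analysis set for the complete-case ANOVA.

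*SAP*

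**What the plan says.** The SAP (Statistical Design and Power) forecasts two groups at the end of the trial. In the program arm, "28 fathers will have completed the program as well as pretests and posttests"; in the other, "28 fathers will have completed pre- and posttests as wait-list controls". Power is then claimed for that sample size with a two-by-two (time by group) repeated measures ANOVA: .95 at d = .50 and r = .50. For d = .33 it says: "Power will be lower but still sufficient (.81) to detect a small/moderate effect size". It adds that "we believe that effect sizes of .40-.50 are likely on each of the primary outcome measures". For implementation measures, "exploratory correlational analyses will be conducted between implementation variables and gain scores on the pre-/posttest measures of program impact".

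In the protocol (Participant Population), the prompt "Provide an estimate of the anticipated participant total" is answered 56. Under Privacy and Confidentiality, fathers uncomfortable with the program are told that "they may choose to stop attending the mentoring program at any time". Under Risks and Benefits, on survey questions: "They are allowed to decline to answer any question they feel uncomfortable with". Under Procedures (Online Surveys), consented fathers in the mentoring group or on the waiting list are sent links to four surveys, four weeks apart. Facilitators record attendance (Participation in the Mentoring Program).

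The supplied text contains no definition of the analysis set, no rule for a missing test or a declined item, and no mapping of the four surveys to pretest and posttest.

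**The concern.** Effectiveness is a primary objective (Study 1 Objective 2). The only description of who will be counted is asymmetric: program fathers must finish the program as well as the tests, whereas wait-list fathers need only the tests. Fathers who leave the program may differ from those who stay, and the wait-list arm has no matching filter.

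With no set stated, the choice between all fathers and program completers can be made after the data are seen. Separately, the named ANOVA drops any father who lacks one of the two scores, so loss would remove fathers by default even if nobody chose a completer analysis.

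**Working it through.** **1. Counts.** SAP: 28 + 28 = 56 completers. Protocol: 56 anticipated. Difference: 56 − 56 = 0. Taken together, the two figures leave no margin between enrolled and completing fathers.

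**2. Who enters the ANOVA.** In a two-by-two repeated measures ANOVA, the time-by-group test equals a two-sample comparison of change scores. A father with only one test has no change score and contributes nothing. The exploratory gain scores have the same requirement.

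**3. Routes to loss.** Declining items can leave a scale score missing. Stopping attendance does not by itself lose survey data, because links go to consented fathers at each time point. Program drop-outs would therefore be lost mainly if program completion were made a condition of analysis, and then from one arm only.

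**4. The SAP's own power.** Inputs: 28 per arm, r = .50, two tests (SAP); alpha .05 two-sided (assumed, since none is stated). Convention: f = d/2, λ = f² × (4·n1·n2/N) × 2/(1 − r), F on 1 and N − 2 df.

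At d = .50: f² = .0625; 4 × 28 × 28/56 = 56; 2/(1 − .50) = 4; λ = .0625 × 56 × 4 = 14.0; power .957, against the stated .95. This reproduces.

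**5. Effect of loss.** The documents give no loss rate. Rates of 10, 20 and 30% are assumed, so 28 becomes 25, 22 or 20.

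| Assumed loss | n (program/wait-list) | λ, d = .50 | Power | λ, d = .40 | Power |
|---|---|---|---|---|---|
| None | 28/28 | 14.0 | .957 | 8.96 | .836 |
| 10%, program arm | 25/28 | 13.21 | .946 | 8.45 | .814 |
| 20%, program arm | 22/28 | 12.32 | .930 | 7.88 | .786 |
| 30%, program arm | 20/28 | 11.67 | .917 | 7.47 | .763 |
| 10%, both arms | 25/25 | 12.5 | .934 | 8.0 | .791 |
| 20%, both arms | 22/22 | 11.0 | .900 | 7.04 | .736 |
| 30%, both arms | 20/20 | 10.0 | .869 | 6.4 | .693 |

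At d = .50, power stays above .80 down to 17 per arm (.807). At d = .40, the low end of what the SAP calls likely, it falls below .80 with a 20% loss in the program arm or a 10% loss in both.

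**6. Limits of these figures.** The same convention gives .68, not .81, at d = .33 (f = .165, λ = 6.10). It also implies a between-group difference in change of 2d, or 1.0 SD at d = .50. If d = .50 instead means a .50 SD difference in change, λ = .25/(2 × .50) × (28 × 28/56) = 3.5 and power is .45 before any loss. These are separate defects and add no weight to this point. They do mean that the table should not be copied into the SAP until the meaning of d is settled.

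**7. Pretest and posttest.** A new group starts each month and wait-listed fathers await the next one. The documents do not say when they start, so some of the four surveys could fall after wait-list fathers have entered the program.

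**The case against.** The completer sentence opens as an anticipation. Basing power on expected evaluable fathers is ordinary practice, and nothing says drop-outs will be excluded. That stands. A reader might infer that the SAP commits to a completers-only analysis; the text does not support this.

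The 56 answers a form prompt for an estimate and is not a cap. It may simply repeat the expected completers. That also stands. A reader might infer that zero attrition is planned, but the supportable statement is only that enrolled and completing fathers are not distinguished.

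The SAP is a single page that refers to a section 4.2 found in neither document, and the grant proposal and data management plan are listed as attachments but were not supplied. The protocol also promises documented syntax for scale scores, where a declined-item rule could sit. The absence is therefore established for the supplied text only.

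The supplied text describes no randomisation. Keeping all fathers in their groups avoids a further selection step but does not make the groups comparable. A likelihood-based model also assumes data missing at random.

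Finally, this is a feasibility pilot with modest power losses, and attendance and survey data would still permit an all-fathers analysis. All true, but effectiveness is named primary and power is claimed for it, so stating the set in advance is a fair and cheap request. What survives is that the only named test is complete-case and no set is given beyond the asymmetric forecast.

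**Conclusion.** The point holds in limited form. The supplied text bases power on 56 completers, equal to the estimated participant total. It names a complete-case test and gives no analysis set, although the protocol foresees fathers leaving the program and declining questions. If the forecast were used as the set, program drop-outs would leave one arm only; the size and sign of the resulting bias cannot be derived from the documents.

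A reader might infer that drop-out would leave the trial seriously underpowered. The figures do not support that at d = .50, where a 20% loss in both arms still leaves .90. At d = .40 the same loss gives .74. Both rest on assumed loss rates, an assumed alpha and the f = d/2 convention, and both are secondary to the missing analysis set. This is a worthwhile correction to make before analysis, not a fatal flaw.

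**What to change.** 1. Make the primary analysis include all consented fathers in their group at survey 1, whatever their attendance. Replace the complete-case ANOVA with a likelihood-based mixed model, or full-information maximum likelihood in Mplus, which the protocol already lists. State that this assumes data missing at random and does not make non-randomised groups comparable. State the rule for declined items and report missing counts by arm.
2. Keep the program-completer analysis as secondary, defined from the attendance records.
3. Name which of the four surveys are pretest and posttest, state when wait-list fathers start the program, and limit the primary contrast to surveys taken before they start.
4. State whether 56 is enrolled or completing. Once alpha and the meaning of d are stated, restate power at the number expected to have both tests.

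**Cost.** SAP wording and a slightly more complex model; no new data. The estimate may be smaller because non-completers count. As an illustration, if 20% of program fathers stop and gain nothing (both assumed), a completer effect of .50 becomes .50 × .80 = .40, with power .836 at 28 per arm on the same convention. Fewer surveys may remain in the contrast, and the stated power will be lower.
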